6.4. Subject Disposition

Subject disposition will be summarized as follows for each part:

• The number of subjects who were consented, who were randomized, and who are in each analysis population will be summarized by treatment group and overall. The number of early termination and the reasons for terminations will be tabulated by treatment group and overall.

6.5. Protocol Deviations

A listing of protocol deviations will be provided within Appendix 16.2.

6.6. Baseline Comparability

The comparability of treatment with respect to subject demographics and baseline characteristics will be assessed in a descriptive manner, but no formal statistical testing will be performed.

Standard continuous or categorical variable summaries will be presented by treatment for the following variables based on the Safety Population.

6.7. Demography

Demography will be tabulated by treatment and overall for each part.

- Age at time of first dose
- Gender (Male, Female)
- Ethnicity (Hispanic or Latino, Not Hispanic or Latino)
- Race
 - White
 - Black or African American
 - Asiar
 - American Indian or Alaska Native
 - Native Hawaiian or Other Pacific Islander
 - Multiple
- Height (cm)
- Body weight (kg)
- BMI (kg/m^2)

Where multiple races have been selected these will be summarized as multiple on the Demographic table, but each race will be listed individually. Social history will be listed.

The following baseline social history summary will also be presented by treatment and overall. Listings will also be provided.

- Tobacco Use frequency (never, former, current).
- Alcohol Use frequency (never, former, current).

6.8. Medical History

Separate listings of previous and ongoing conditions at screening will be presented for the Safety Population. Conditions will be coded using the Medical Dictionary of Regulated Activities (MedDRA) primary system organ class and preferred term.

6.9. Prior and Concomitant Medications

Prior and concomitant medications will be listed for the Safety Population. Prior medications are defined as all medications starting before the date of first dose of study drug. Concomitant medications are defined as medications taken on or after the date of first dose of study drug and will be coded using the WHODrug dictionary.

6.10. Exposure to Study Drug

For Part B, extent of exposure (number of days of exposure to study drug) will be presented by treatment for the Safety Population. All dosing information will be listed.

[figure not shown]
6.11. Pharmacokinetic and Statistical Analyses

Pharmacokinetic analyses are outlined below. Other exploratory analyses may be conducted as well.

Statistical Comparison: Single Dose (Day 1, Reference) and Multiple Dosing (Day 7, Test): Part B

Comparison of the log-transformed pharmacokinetic parameters C_{max} and AUC_{0-24} for PK10571 across study days (Day 7 vs. Day 1) will be performed using an ANOVA model and the two one-sided t-tests procedure. The ANOVA model will include factors for subject, day, and cohort. The ratios of the geometric means and 95% confidence intervals will be reported. Statistical analyses will be performed using appropriate software, e.g., PhoenixTM WinNonlin® (Version 6.3 or higher, Certara L.P.) and/or SAS® (Version 9.3 or higher, SAS Institute Inc.).

SAS code will be of the form:

Assessment of Dose-proportionality: Power Model

The relationship between dose and exposure parameters will be examined graphically for Part A (C_{max}, AUC_{last}, AUC₀₋₂₄, and AUC_{inf}) and Part B (C_{max} and AUC₀₋₂₄, Days 1 and Day 7).

Evaluation of dose proportionality will be explored using power analysis.

To assess dose proportionality, the pharmacokinetic parameters after drug administration will be compared across each dose level.

Statistical analyses will be done using a power model with mixed effects (Smith, 2000)³ of the following general form:

$$ln(PK) = ln(\beta_0) + \beta_1 \cdot ln(Dose) + \varepsilon$$
,

where

PK is the pharmacokinetic parameter tested (e.g., C_{max} or AUC),

 $ln(\beta_0)$ is the y-intercept,

 β_1 is the slope (a value of $\beta_1 \approx 1$ indicates linearity), and

ε is an error term.

The estimate of slope, $\beta 1$ will be reported along with the corresponding 2-sided 95% CIs. As this is an exploratory analysis, if the 95% CI of β_1 includes 1 and/or the estimate of β_1 is relatively close to 1, PK data may appear to be dose proportional.

The SAS code will be of the form:

The Attainment of Steady-State:

The attainment of steady-state will be assessed by visual inspection of trough concentrations, and statistical assessment. For statistical assessment, linear regression of the individual trough concentrations on Days 3-7 vs time will be conducted, and the slope, 95% CI of the slope, and p-value will be estimated. If the 95% CI of the slope includes 0 and/or the estimate of slope is relatively close to 0, steady-state may appear to be reached.

Exploratory Analyses: Scatterplots

To assess relationships between PK10571 PK parameters and baseline characteristics, scatterplots will be created as outlined below.

Baseline is defined as the last non-missing value (either scheduled, unscheduled or repeat) before the subject receives the first dose of study drug in both Part A and Part B.

Scatterplots for Part A (SAD) (y-axis vs x-axis)

- C_{max}, AUC₀₋₂₄, AUC_{last}, AUC_{inf}, and T_{1/2} vs baseline FVC.
- C_{max}, AUC₀₋₂₄, AUC_{last}, AUC_{inf}, and T_{1/2} vs baseline FEV1.
- C_{max}, AUC₀₋₂₄, AUC_{last}, AUC_{inf}, and T_{1/2} vs. body size (baseline body weight and BMI).
- C_{max}, AUC₀₋₂₄, AUC_{last}, AUC_{inf}, and T½ vs gender. C_{max} and AUC values will be presented with and without weight-adjustment.
- CL/F and V_z/F vs baseline FVC.
- CL/F and V_z/F vs baseline FEV1.
- CL/F and V_z /F vs. body size (baseline body weight and BMI).
- CL/F and V_z/F (with and without weight-adjustment) vs gender.

Scatterplots for Part B (MAD):

- C_{max}, AUC₀₋₂₄, and T_{1/2} vs baseline FVC.
- C_{max} , AUC₀₋₂₄, and $T_{\frac{1}{2}}$ vs baseline FEV1.
- C_{max} , AUC₀₋₂₄, and $T_{\frac{1}{2}}$ vs body size (baseline body weight and BMI).
- C_{max}, AUC₀₋₂₄, and T_½ vs gender. C_{max} and AUC values will be presented with and without weight-adjustment.
- CLss/F and V_z/F vs baseline FVC.
- CLss/F and V_z/F vs baseline FEV1.
- CLss/F and V_z /F vs body size (baseline body weight and BMI).
- CLss/F and V_z/F (with and without weight-adjustment) vs gender.

For all the scatterplots, different symbols will be used for different dose cohorts. For MAD, $T_{\frac{1}{2}}$, CLss/F, and V_z /F values are for Day 7 only.

For C_{max} and AUC: weight-adjusted PK parameter = PK parameter × body weight in kg/70.

For CL and V: weight-adjusted PK parameter = PK parameter × 70/body weight in kg.

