### **3 STUDY DESIGN SUMMARY**

This is a first-in-human, single-center, randomized, double-blind, placebo-controlled, two-part study in healthy adult males and females of non-childbearing potential. Because the safety profile of PK10571 in humans is unknown and this is the first clinical study to assess PK10571 in humans, a single-ascending dose escalation design will be used in Part A of the study. Part B will be a multiple-ascending dose escalation design, to be run only after review of safety and pharmacokinetic data from Part A.

In the single ascending dose study (Part A) at least 4 dose levels of PK10571 will be tested:

An optional fifth dose level of up to may be added, based on safety and pharmacokinetic data from the first 4 cohorts. Subjects will be randomized into one dose cohort and receive either PK10571 or placebo. Within each cohort, 6 subjects will receive active drug and 2 subjects will receive placebo.

In the multiple ascending dose study (Part B), up to three dose levels of PK10571 will be tested. The daily dose will be administered daily for 7 days with close clinical monitoring. The dose for the first cohort of Part B will be determined by review of the safety and pharmacokinetic data from Part A by the Safety Review Committee. The dose interval for the first cohort of Part B (i.e., once daily, twice daily, or up to three times daily) will be determined by review of the safety and pharmacokinetic data from Part A by the Safety Review committee. Subsequent doses and dosing intervals will be determined by review of the safety and pharmacokinetic data from the prior cohort.

For both Part A and Part B, for each cohort, randomization will occur in 2 blocks as follows: In the first block, 2 subjects (sentinel subjects) will be randomized 1:1 to receive PK10571 or placebo; in the second block, 6 subjects will be randomized 5 PK10571: 1 placebo. If PK10571 is well-tolerated in the sentinel subjects, the remainder of the cohort (n = 6) will be randomized. There will be a minimum of 48 hours between dosing of the 2 sentinel subjects and the remainder of the cohort.

The safety, tolerability, and pharmacokinetics of PK10571 will be evaluated in each sequential cohort prior to each dose cohort escalation, assessing the totality of all the safety data prior to initiating the next cohort.

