### 3.2 Part B

Part B is a multiple ascending dose study design. Subjects will receive either PK10571 or placebo. Approximately 24 subjects will be enrolled in Part B. Subjects will be enrolled in 3 cohorts of 8 subjects each.

Gossamer Bio, Inc.

The initial dose for Part B will be determined after review of the safety and pharmacokinetic data from Part A by the Safety Review Committee.

Data from the lower dose cohort will be analyzed before deciding whether to proceed with the higher dose cohort. Alternatively, a lower dose may be administered, depending upon review of previous cohort's safety and pharmacokinetic data.

Subjects will receive one of the treatments listed in Table 3. The assigned treatment will be given either as a single daily dose (QD), or divided into two daily doses (BID), or divided into three daily doses (TID; each dose to be separated by 6 hours on a given day).

Subjects will be assigned to either active treatment or placebo in randomized fashion.

Table 3Part B: Planned Doses for Cohorts 1–3

| Cohort                 | Test Formulation (n = 6) | Placebo (n = 2) |
|------------------------|--------------------------|-----------------|
| 1                      | PK10571 initial dose     | Placebo         |
| 2                      | PK10571 mid dose*        | Placebo         |
| 3                      | PK10571 high dose*       | Placebo         |
| n = number of subjects |                          |                 |

n = number of subjects

Note: The dosing regimen will be either once daily (QD), twice daily (BID), or three times daily (TID) for 7 consecutive days. For TID dosing, each daily administration will be separated by 6 hours.

\* Alternately, Cohort 2 or 3 will receive a lower dose, depending upon safety and pharmacokinetic data from Cohort 1 or 2, respectively.

Each dose will be administered using an oral inhalation device. Meals will be the same and scheduled at approximately the same times relative to dose for each cohort, if possible. Refer to Section 5.5.1 for details regarding timing of meals for each proposed dosing regimen (QD, BID, and TID).

No water may be consumed for 1 hour prior through 1 hour after each dose, except for 60 mL of room temperature water which will be given to subjects to rinse their mouths after dosing. Subjects will swish the 60 mL of water in their mouths then spit it out.

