## APPENDIX 4 PART B: MAD TWICE DAILY (BID) DOSING

The Safety Review Committee will review the safety data (including local irritation) and pharmacokinetic data from the SAD protocol (Part A) to determine the starting dose for the first MAD cohort and if the first cohort of the MAD protocol should be dosed QD (once daily), BID (twice daily; once every 12 hours), or TID (three times daily; 6 hours between each dose for a given day of dosing).

If the decision is made to start dosing in the MAD protocol at BID, then the Safety Review Committee will review the safety data (including local irritation) and PK data from the first MAD cohort to determine if BID dosing should continue, if dosing should be reduced to QD, or if dosing should be increased to TID for the next cohort.

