## APPENDIX 5 PART B: MAD THREE TIMES DAILY (TID) DOSING

The Safety Review Committee will review the safety data (including local irritation) and pharmacokinetic data from the SAD protocol (Part A) to determine the starting dose for the first MAD cohort, and if the first cohort of the MAD protocol should be dosed QD (once daily), BID (twice daily; once every 12 hours), or TID (three times daily; 6 hours between each dose).

If the decision is made to start dosing in the MAD protocol at TID, then the Safety Review Committee will review the safety data (including local irritation) and PK data from the first MAD cohort to determine if TID dosing should continue, if dosing should be reduced to BID or QD for the next cohort. Similarly, if the starting dose in the MAD protocol is BID, then the Safety Review Committee will review the safety data (including local irritation) and PK data from the first MAD cohort to determine if BID dosing should continue, or if dosing should be changed to QD or TID for the next cohort.

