6.2.10. Concentration-Time Data

PART A:

Blood samples for pharmacokinetic analysis of PK10571 will be collected at 0 hour (predose), and then at 3, 10, 20, 30, 40 minutes, and 1, 2, 4, 8, 12, 24, 36, and 48 hours after study treatment administration as specified by the protocol amendment. For two blood samples were collected at 1 and 5 minutes, instead of one blood sample at 3 minutes, prior to the protocol amendment. For and above, the 3-minute sample was collected after the protocol amendment.

PART B:

If QD dosing: Blood samples for pharmacokinetic evaluation will be obtained prior to the first dose administration (predose) on Day 1 and Day 7, and at the following times: Day 1 and Day 7 at 3, 10, 20, 30, and 40 minutes and 1, 2, 4, 8, 12, 24, and 36 hours after dosing; predose on Days 3-6, and on Day 8, Day 9, Day 10, Day 14, and Day 35 (total 34 samples).

If BID dosing: Blood samples for pharmacokinetic evaluation will be obtained prior to the first dose administration (predose) on Day 1 and Day 7, and at the following times after each dose (2 per day) on Day 1 and Day 7: 3 and 30 minutes and 2, 8, and 12 hours. Blood samples will also be collected before the first dose on Days 3-6, and on Day 8, Day 9, Day 10, Day 14, and Day 35 (total of 30 samples).

If TID dosing: Blood samples for pharmacokinetic evaluation will be obtained prior to the first dose administration (predose) on Day 1 and Day 7, and at the following times after each dose (3 per day) on Day 1 and Day 7: 3 and 40 minutes and 6 hours. An additional sample will be obtained on Day 2 (12 hours after the 3rd dose on Day 1). Blood samples will also be collected before the first dose on Days 2-6, and on Day 8 (6 hours and 12 hours after the 3rd dose on Day 7), Day 9, Day 10, Day 14, and Day 35 (total of 30 samples).

For multi-capsule administrations (if required to achieve the dose), the first postdose blood collection will be performed 5 minutes after the start of study treatment administration.

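### SAP 6.11 fits one undefined Dose to Part B Cmax and AUC0-24; if dosing frequency differs between cohorts, the pooled Cmax slope can miss 1 even when exposure is exactly dose-proportional

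*SAP*

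**What the plan says.** SAP 6.11 introduces the assessment with "the pharmacokinetic parameters after drug administration will be compared across each dose level" and then states: "Statistical analyses will be done using a power model with mixed effects". The printed form is ln(PK) = ln(β0) + β1·ln(Dose) + ε. The list beneath it explains PK, the intercept, the slope and the error, but not Dose. The same form covers Part B Cmax and AUC0-24 on Days 1 and 7. If the 95% CI for β1 includes 1, or the estimate is near 1, the SAP reads this as apparent proportionality. It prefaces that rule with "As this is an exploratory analysis".

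Protocol 3.2 describes Part B dosing this way: "The assigned treatment will be given either as a single daily dose (QD), or divided into two daily doses (BID") or into three (TID, 6 hours apart). Protocol Section 3 adds: "Subsequent doses and dosing intervals will be determined by review of the safety and pharmacokinetic data from the prior cohort". Appendix 4 has the Safety Review Committee decide, after a BID first cohort, whether to stay on BID, "if dosing should be reduced to QD, or if dosing should be increased to TID for the next cohort". Appendix 5 repeats this for a BID start ("or if dosing should be changed to QD or TID for the next cohort") and allows a TID start to be reduced to BID or QD.

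The SAP names a Part B dose basis in one formula: CLss/F in Section 6.2.11 divides the total daily dose by AUC0-24.

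**The concern.** Under BID or TID the total daily dose and the dose per administration differ two- or three-fold. AUC0-24 at steady state follows the daily total. Cmax follows mainly the single administration, plus whatever is left from earlier doses. If cohorts use different frequencies, one Dose variable generally cannot suit both parameters, and a slope away from 1 may reflect how the daily amount was split and not the drug.

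Dose-linearity is listed among the PK endpoints in SAP 3.1, and Part B has its own output, Table 14.4.19. The Part B table titles identify cohorts by FPD without the regimen or the dose basis, so a reader could take a Cmax slope well below 1 as less-than-proportional exposure.

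**Working it through.** **Inputs from the documents.** Up to three Part B cohorts with 6 active subjects each; doses at 0 h (QD), at 0 and 12 h (BID), or at 0, 6 and 12 h (TID); benchmark β1 = 1 with a two-sided 95% CI.

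**Assumptions, because the documents show no values.** Exact dose proportionality; daily doses 1:2:4; half-life h of 2, 6, 12 or 24 h; one compartment with instantaneous absorption; Cmax is the highest peak of the day.

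**Step 1: the SAP's benchmark.** With one regimen in all cohorts, the slope is 1.00 for both parameters, on both days and on either dose basis. The benchmark is right in that case.

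**Step 2: Cmax on total daily dose.** Let g be the peak per unit of daily dose.
- QD: g = 1
- BID: g = (1 + 2^(−12/h))/2
- TID: g = (1 + 2^(−6/h) + 2^(−12/h))/3

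Carry-over from earlier days multiplies every regimen by the same factor, so Day 1 and Day 7 slopes agree. The log doses are equally spaced, so the least-squares slope depends only on the first and third cohorts: slope = 1 + ln(g3/g1)/ln 4.

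Example, QD-BID-BID at h = 6: g3 = (1 + 0.25)/2 = 0.625, and the slope is 1 + ln(0.625)/1.386 = 0.66.

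| Sequence | h = 2 | h = 6 | h = 12 | h = 24 |
|---|---|---|---|---|
| QD-BID-BID | 0.51 | 0.66 | 0.79 | 0.89 |
| BID-QD-QD | 1.49 | 1.34 | 1.21 | 1.11 |
| BID-BID-TID | 0.79 | 0.95 | 0.99 | 1.00 |
| QD-BID-QD | 1.00 | 1.00 | 1.00 | 1.00 |

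**Step 3: AUC0-24 on total daily dose.** On Day 7 the slope is 1.00 for every sequence in the table. On Day 1 part of a divided dose falls outside the 24 h window. At h = 24 the AUC per unit of daily dose is proportional to 1 − 0.5 = 0.5 for QD and to 1 − (0.5 + 0.707)/2 = 0.396 for BID. The QD-BID-BID slope is then 1 + ln(0.396/0.5)/1.386 = 0.83; for BID-QD-QD it is 1.17.

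**Step 4: the other dose basis.** Against dose per administration, the Day 7 AUC0-24 slope is 1.50 for QD-BID-BID (ln(1, 2, 4) on ln(1, 1, 2)), 1.34 for BID-BID-TID and 0.75 for QD-BID-QD. Per-administration dose is therefore no common solution.

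**Step 5: would the SAP's CI show it?** Simulation used 40,000 trials per case, n = 18, log-normal error with SD = √ln(1 + CV²), and t intervals on 16 df. The entries are the percentage of trials in which the 95% CI for the QD-BID-BID Cmax slope excludes 1; the nominal rate is 5%.

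| CV | h = 2 | h = 6 | h = 12 | h = 24 |
|---|---|---|---|---|
| 30% | 93 | 69 | 34 | 14 |
| 50% | 60 | 35 | 16 | 8 |
| 70% | 39 | 22 | 11 | 7 |

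For BID-BID-TID the rate is 5 to 7% at half-lives of 6 h and above.

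**Step 6: the scheduled samples.** QD is sampled on "Day 1 and Day 7 at 3, 10, 20, 30, and 40 minutes" and at later times. BID has only 3 and 30 min before 2 h, and TID only 3 and 40 min before 6 h. Assuming first-order absorption with Tmax at 5 or 10 min, a linear trapezoid and half-lives of 2 to 24 h, the sampled Day 7 AUC0-24 slope on daily dose is 0.99 to 1.06 (QD-BID-BID), 0.94 to 1.01 (BID-QD-QD) and 0.99 to 1.09 (QD-BID-TID). It is close to 1.00 but not guaranteed to equal it.

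**The case against.** The strongest reply has four parts.

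1. **The evidence is partial.** SAP 6.11 announces SAS code that is absent from the supplied text, and the equation is offered as a general form. A reader might infer that the fitted model has no regimen term. The documents do not support that inference, because a dose variable, a BY statement or a regimen factor could stand in the code. What stands is narrower: the printed equation leaves Dose undefined.
2. **Daily dose is the natural basis for AUC0-24.** Protocol 3.2 speaks of a daily treatment that is divided, and CLss/F uses the total daily dose over the same AUC. This is right. On that reading Day 7 AUC0-24 is sound, and the slopes of 1.50, 1.34 and 0.75 do not arise. The difficulty is left with Cmax, and with Day 1 AUC0-24 at longer half-lives.
3. **Regimens may never differ.** A change is permitted, not planned, and Protocol 1.3 even speaks of once-daily dosing. The appendices spell out switches from a BID or TID start; a switch after a QD start rests on the general sentence in Section 3. BID-BID-TID, which Appendix 4 does spell out, shows little distortion from 6 h upward. BID-QD-QD, equally permitted, shows as much as QD-BID-BID. This limits the point but does not remove it.
4. **Little rests on the result.** The rule is soft, graphs are planned as well, and SAP 6 allows added analyses in the study report. This stands, and it sets the severity.

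**Conclusion.** The point holds as a minor, conditional one. If Part B cohorts use different frequencies, the pooled Cmax slope on total daily dose can depart from 1 under exact proportionality. Its size depends on the sequence and on the assumed half-lives and 1:2:4 doses: from 0.51 (QD-BID-BID, 2 h) to 1.49 (BID-QD-QD, 2 h), shrinking toward 1 as the half-life lengthens. Day 7 AUC0-24 on total daily dose is unaffected apart from sampling error.

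A reader might infer more, and three such readings fail. Cmax does not always fail: QD-BID-QD stays at 1.00. The Part B assessment is not biased in every case: with one shared regimen there is no bias. Dose escalation is not shown to depend on the slope: the power model is not among the interim items in SAP 7. The Part A assessment is untouched.

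**What to change.** In SAP 6.11:
- Define Dose as total daily FPD for AUC0-24, matching CLss/F.
- If regimens differ, base the pooled Part B assessment on Day 7 AUC0-24 only.
- Fit Cmax and Day 1 AUC0-24 only among cohorts that share a regimen; otherwise describe them.
- Show the regimen and total daily FPD in the Part B table titles.

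This costs SAP wording and table titles, with no extra subjects or samples, and changes no result if all cohorts share a regimen. The downside is that a mixed Part B may yield no pooled Cmax slope.

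A Day 1 first-dose Cmax fit on dose per administration is optional. It adds a parameter that SAP 6.2.11 does not list, and it narrows the dose range. At CV 30% the 95% CI half-width is 2.12 × 0.294/√Sxx, where Sxx is the sum of squared deviations of ln(Dose) over the 18 subjects. This gives 0.26 on daily doses 1:2:4 (Sxx 5.77), 0.45 on 1:1:2 for QD-BID-BID (Sxx 1.92) and 1.08 on 1:1:1.33 for QD-BID-TID (Sxx 0.33). With TID included it is not useful: at an assumed Tmax of 10 min and half-lives of 1 to 24 h, the sampled slope for QD-BID-TID runs from 0.25 to 0.97, against 0.86 to 0.99 for QD-BID-BID.

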3. ENDPOINTS

3.1. Primary Endpoint

The safety endpoints are the incidence of treatment-emergent events (TEAEs), physical examination findings, and changes in vital signs, pulmonary function and electrocardiogram (ECG) measurements.

Pharmacokinetic (PK) endpoints are the summary of the pharmacokinetic parameters (e.g. C_{max}, AUC_{last}, and AUC_{inf}) for PK10571 across treatments, dose-linearity assessment and steady state assessment (after multiple dosing)

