5. RANDOMIZATION

Subjects will be randomized into one dose cohort and receive either PK10571 or placebo. Within each cohort, 6 subjects will receive active drug and 2 subjects will receive placebo.

For both the SAD and MAD parts each cohort, randomization will occur in 2 blocks as follows: In the first block, 2 subjects (sentinel subjects) will be randomized 1:1 to receive PK10571 or placebo; in the second block, 6 subjects will be randomized 5 PK10571: 1 placebo. If PK10571 is well-tolerated in the sentinel subjects, the remainder of the cohort (n = 6) will be randomized. There will be a minimum of 48 hours between dosing of the 2 sentinel subjects and the remainder of the cohort.

Gender distribution will be based on sequential screening of volunteers who meet entry criteria, with a minimum of 4 females per cohort, in order to ensure 2 females per active dose group. Subjects will be assigned numbers in an ascending order, based on successful completion of the screening process. Each subject will participate in only one cohort.

Subjects who withdraw from the study may be replaced at the discretion of the Principal Investigator and Sponsor.

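### The Part B steady-state regression stops at the Day 7 predose trough, although every regimen already collects an equivalent trough 24 h after the first Day 7 dose; adding it is a free but optional gain in precision.

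*SAP*

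**What the plan says.** SAP 3.1 lists among the PK endpoints a "dose-linearity assessment and steady state assessment (after multiple dosing"). SAP 6.11 assesses steady state in two ways. One is visual inspection of troughs, with no day range given. The other is statistical: "linear regression of the individual trough concentrations on Days 3-7 vs time will be conducted". This yields a slope with a p-value and a 95% interval. The reading rule is "If the 95% CI of the slope includes 0 and/or the estimate of slope is relatively close to 0, steady-state may appear to be reached". The SAP does not say whether the line is fitted per cohort, across cohorts or per subject.

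SAP 6.2.10 sets the sampling, and Protocol Appendix 1 agrees. For QD, Day 1 and Day 7 samples run to "1, 2, 4, 8, 12, 24, and 36 hours after dosing; predose on Days 3-6, and on Day 8, Day 9" and later visits; the list ends "on Day 8, Day 9, Day 10, Day 14, and Day 35 (total 34 samples"). For BID, the last sample after each dose on Days 1 and 7 is at 12 h. For TID, samples include "Day 8 (6 hours and 12 hours after the 3rd dose on Day 7"). Dosing lasts 7 consecutive days. On group size, SAP 5 says: "Within each cohort, 6 subjects will receive active drug and 2 subjects will receive placebo".

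**The concern.** The regression asks whether troughs are still rising. Its last point is drawn just before the Day 7 dose, so it ends where the Day 7 dosing interval begins. AUC0-24, Cavg,ss and CLss/F on Day 7 all describe that interval. The trough that closes it is scheduled in every regimen, but the regression as written does not use it.

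The direction of the lost precision also matters. The rule treats a CI that includes 0 as support for steady state, so a wider interval makes that reading easier to reach. With 6 active subjects per cohort the interval is already wide. The SAP gives no reason for stopping at Day 7.

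**Working it through.** **Step 1. Is the Day 8 sample an equivalent trough?**

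| Regimen | Last dose before a Days 3-7 trough | Matching sample after Day 7 | Time since last dose |
|---|---|---|---|
| QD | previous morning | 24 h after the Day 7 dose | 24 h |
| BID (every 12 h, Protocol Appendix 4) | dose 2, the evening before | 12 h after dose 2 on Day 7 | 12 h |
| TID (doses at 0, 6 and 12 h) | dose 3, the evening before | 12 h after dose 3 on Day 7 | 12 h |

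Each matching sample falls 24 h after the first Day 7 dose, and no Day 8 dose precedes it. This takes the first dose of each day to be at the same clock time.

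**Step 2. Do the stated sample totals agree?** The SAP states 34 (QD), 30 (BID) and 30 (TID).

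- QD: 2 predose + 2 x 12 postdose + 4 (Days 3-6) + 4 (Days 9, 10, 14, 35) = 34. Counting Day 8 as a further draw gives 35.
- BID: 2 + 2 x 2 x 5 + 4 + 4 = 30. Counting Day 8 separately gives 31.
- TID: 2 + 2 x 3 x 3 + 1 (Day 2, 12 h after dose 3) + 4 (Days 3-6) + 1 (Day 8, 12 h after dose 3) + 4 = 30.

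All three totals are reproduced with the Day 8 trough counted once. For QD and BID it is the last scheduled postdose sample at 24 h after the first dose.

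**Step 3. Effect on the CI.** The half-width of the slope CI is t(0.975, df) x sigma / sqrt(n x Sxx), where sigma is the residual SD and Sxx is the sum of squares of day about its mean.

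- Days 3-7: mean 5, Sxx = 4+1+0+1+4 = 10.
- Days 3-8: mean 5.5, Sxx = 2 x (6.25+2.25+0.25) = 17.5.
- SE ratio: sqrt(17.5/10) = 1.323.

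| Fit | df (Days 3-7, Days 3-8) | Half-width in sigma/day, Days 3-7 | Half-width, Days 3-8 | Ratio |
|---|---|---|---|---|
| One cohort, n = 6, pooled | 28, 34 | 2.048/sqrt(60) = 0.264 | 2.032/sqrt(105) = 0.198 | 1.333 |
| One cohort, subject intercepts | 23, 29 | 2.069/sqrt(60) = 0.267 | 2.045/sqrt(105) = 0.200 | 1.338 |
| One line per subject | 3, 4 | 3.182/sqrt(10) = 1.006 | 2.776/sqrt(17.5) = 0.664 | 1.516 |

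Pooling three cohorts gives 1.326 to 1.328. In the pooled one-cohort fit, adding Day 8 narrows the interval by 1 - 0.198/0.264 = 25%.

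**Step 4. Departures from the simple model (assumed values).** Let r be the between-subject variance of the slope divided by the residual variance. The SE ratio is sqrt((r + 1/10)/(r + 1/17.5)): 1.28 at r = 0.01, 1.18 at r = 0.05 and 1.13 at r = 0.1. First-order serial correlation of 0.3 to 0.5, allowed for in the fit, gives 1.28 to 1.24.

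**Step 5. Effect on power to detect non-steady state (assumed model).** Take ln trough on Day d as a constant plus ln(1 - exp(-24k(d-1))), with k = ln(2)/half-life. Use a within-subject CV of 30%, so sigma = sqrt(ln 1.09) = 0.294, with subject intercepts and n = 6. The slope SE is 0.294/sqrt(60) = 0.0379 for Days 3-7 and 0.294/sqrt(105) = 0.0287 for Days 3-8. Power is from the noncentral t distribution at the two-sided 5% level.

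| Half-life | True slope/SE, Days 3-7 | True slope/SE, Days 3-8 | Power, Days 3-7 | Power, Days 3-8 |
|---|---|---|---|---|
| 12 h | 0.378 | 0.371 | 0.065 | 0.065 |
| 24 h | 1.70 | 1.78 | 0.372 | 0.406 |
| 36 h | 2.81 | 3.06 | 0.768 | 0.840 |
| 48 h | 3.59 | 3.99 | 0.930 | 0.971 |

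The gain is smaller than the CI ratio suggests because the later point lies nearer the plateau. At 24 h, for example, the true slope falls from 0.0646 to 0.0510 per day.

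**The case against.** The strongest reply is that interval width is the wrong yardstick: what matters is how often non-steady state is detected. On that measure the gain is small. At half-lives of 12 h or below, slope/SE is marginally lower with Day 8 (ratio 0.98 at 12 h, about 0.95 at 6 h). If steady state truly holds, the 95% CI covers 0 equally often either way. The documents give no human half-life. Protocol 1.1.1 reports that accumulation did not appear to be an issue in rats or dogs, which points away from the long half-lives where the gain appears, though it does not settle the human value. All of this stands. The loss at short half-lives is immaterial, because power there is about 0.05 to 0.07 with either set of days.

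It can also be said that Days 3-7 is a coherent choice: consecutive predose samples, each followed by a dose, the same in every regimen. That stands too, and is why this is not an error. The looser parts of the rule (the and/or, and a slope relatively close to 0) are untouched by a sixth point.

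Some stronger readings are tempting but unsupported:

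- *The omission costs as much as 75% more subjects would bring.* That is true of the SE (17.5/10 = 1.75) but not of power. At a 24 h half-life, power is 0.37 with Days 3-7 and 0.41 with Day 8 added, but about 0.60 with 75% more subjects.
- *Day 8 is the single most influential point.* Days 3 and 8 are both 2.5 days from the mean, so their leverage is equal.
- *The steady-state parameters hang on this test.* SAP 6.2.11 defines Cavg,ss and CLss/F for Day 7 unconditionally.
- *The sample is discarded.* It is left out of the regression only; it still closes the Day 7 AUC0-24.
- *The trough tables omit Day 8.* The titles of tables 14.4.7 and 14.4.8 name no days, so this cannot be told.

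**Conclusion.** The point holds as an optional improvement. An equivalent Day 8 trough is scheduled in all three regimens and the regression does not use it. For one cohort of 6 active subjects with complete troughs, independent equal-variance residuals and a common slope, the planned slope CI is about one third wider than the collected data allow. Under the assumed slope variation (r up to 0.05) or serial correlation, the SE is about 18 to 28% wider, and larger slope variation shrinks this further. If a line is fitted per subject, the CI is about 52% wider.

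The practical consequence is modest: 3 to 7 percentage points of power at assumed half-lives of 24 to 48 h under a log-trough model with 30% CV, and essentially nothing at 12 h or below. The SAP regresses trough concentrations and mentions no log, so the power figures are illustrative.

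A reader might infer that the plan's steady-state conclusion is unsound as it stands. The documents do not support that: the wording is descriptive, visual inspection runs alongside, and no parameter, analysis or dose decision is conditional on the slope.

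**What to change.** In SAP 6.11, change the regression window from Days 3-7 to *Days 3-8, where Day 8 is the sample 24 h after the first Day 7 dose* (QD 24 h postdose; BID 12 h after dose 2; TID 12 h after dose 3). State that trough tables 14.4.7 and 14.4.8 include that sample.

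The cost is one changed sentence and one clarifying statement in the SAP. No sample, assay, subject or visit is added.
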